8.2 Primary Performance Measure

The primary performance measure is MR reduction to $\leq 2+$ at 30 days and 12 months. The count and percentage of patients who are in each severity category will be summarized.

8.3 Secondary Measures

Safety Measures

All AEs and SAEs with onset on or after the procedure date (Day 0) will be summarized using type of event by early events (≤ 30 days) and late events (> 30 days). Summaries of incidence rates (counts and percentages) will be prepared, where data is available.

Functional and Quality of Life Measures

Quality of Life (QoL) as measured by EQ-5D and KCCQ, will be scored according to algorithms provided by the vendor. The various summary scores produced by the algorithms will be analyzed as continuous variables. EQ-5D and KCCQ overall summary scores, and their changes from baseline to 30 days and 12 months will be summarized. Patients that are missing a baseline or follow up values will be excluded from the analysis.

 Edwards	Revision Date: August 22, 2019		Rev	1.0	For Use Only by Affiliates of Edwards Lifesciences	Page 13 of 13
	Title	Statistical Analysis Plan for PASCAL Registry				

Count and percentage of patients in each NYHA Class will be summarized. Change from baseline will be presented as a shift from baseline to 30-day and 12-month follow-up. Patients that are missing baseline or follow-up values will be excluded from the paired analysis.

Summary statistics, including mean, median, SD, and sample size, for 6MWT will be presented. Change in 6MWT at 30 days and 12 months over baseline will be summarized. Patients that are missing baseline or follow-up values will be excluded from the paired analysis. Patients unable to perform the walk due to a medical reason will be considered to have walked a distance of 0 m.

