Data Collection	
Patient data, as per the CRF, will be collected.
 
Clinical and echocardiographic data available from routine clinical records will be captured at the following time points:
 
 • Baseline: pre-procedural data • Procedural data: data collected as part of the procedure • Discharge data: data collected prior to discharge from hospital • 30 day visit: visit performed between discharge and up to 2 months post procedure • 1 year follow up: visit performed between 10 months and 14 months post procedure
Number of Patients	A minimum of 200 patients will be enrolled in the Registry.
Number of Medical Centers	A minimum of 10 sites in the European Union.
Outcome Measures	
Primary Safety Measures:
 
 • Major Adverse Events (MAE) at 30 days. MAEs – composite of all-cause death, Myocardial Infarction, Stroke, Heart Failure Hospitalization, or complication requiring transcatheter or surgical intervention (repeat PASCAL or Mitral Valve Surgery) 
Primary Performance Measure:
 
 • MR reduction to ≤2+ at 30 days and 12 months 
Secondary Measures:
 
 1. Adverse event assessment (all follow up visits) 2. EQ-5D-5L or KCCQ at baseline, 30 days and 12 months, if available 3. 6MWT at baseline, 30 days, and 12 months, if available 4. NYHA assessment at baseline, 30 days and 12 months, if available

Statistical Analysis	No predefined statistical hypothesis testing will be performed. Only descriptive and summary statistical analysis will be provided for baseline/pre-procedure, procedure, and other follow-up outcome variables.
Enrollment Criteria (Inclusion)	
Patients must meet ALL of the following criteria to be eligible for the registry:
 
1. Patients electively treated or electively intended to be treated with Edwards PASCAL Transcatheter Valve Repair System2. Patients provided written informed consent to participate in the registry.
Enrollment Criteria (Exclusion)	
Patients will be excluded from the Registry if they meet the following:
 
1. Patient is part of an ongoing Edwards Pre or Post Market Clinical study for the PASCAL Transcatheter Valve Repair System.

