3.7 Registry Exit Criteria and Procedures

The reason for exit from the registry will be documented on the appropriate case report forms and in the medical records for each patient who exits the registry.

Patients may exit the registry for any of the following reasons:

- Completion per Protocol
- Withdrawal
 - Patient Withdrawal: The patient may voluntarily withdraw from the registry at any time, without penalty or loss of benefits to which they are otherwise entitled.
 - Physician Withdrawal: The Investigator also has the right to withdraw a patient if s/he feels it is in the best interest of the patient to do so.
 - Sponsore Withdrawal: The Sponsor may prematurely terminate the Registry.
- Death
- Device Reintervention or Explant
 - Patients who have a surgical reintervention where the device is explanted will be followed for 30 days post-reintervention or until resolution of any adverse events related to the procedure and then exited from the registry. Patients that have a percutaneous or surgical reintervention where the device remains in place will continue to be followed for the duration of the registry.

- Lost to Follow-up
 - If a patient cannot be reached for a follow-up visit, the Investigator will document the contact efforts made to the patient and/or effort to obtain hospital records in the appropriate electronic case report form. If the patient cannot be reached in any way, or misses a visit, the patient will be considered “unable to contact” for that time interval. After three (3) documented unsuccessful attempts to make contact prove unsuccessful, a certified letter will be sent to the patient’s residence. If there is no response after the certified letter is sent, the patient will be considered “lost to follow-up”.
 - For patients who are lost-to-follow-up or withdraw early, Edwards may request the site to search death registries as available or applicable per GDPR requirements and may request the site to obtain the death certificate, if applicable.

In all cases of withdrawal (as described above), no additional data will be collected.

All data collected up until the time of withdrawal will be analyzed and will be retained for the duration of the registry.

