2.2 Overall Study Design and Plan

This is a post market, prospective and retrospective (where applicable), observational, single-arm, multicenter, registry study of the Edwards PASCAL Transcatheter Valve Repair System for the percutaneous reconstruction of patients with an insufficient mitral valve.

A minimum of 200 patients will be enrolled in the registry at over 10 sites in the Europe.

Patients will be treated per standard of care at their medical facilities and a written informed consent will be obtained to allow the data to be collected. This registry will enroll patients

[REDACTED]

 Edwards	Revision Date: August 22, 2019		Rev	1.0	For Use Only by Affiliates of Edwards Lifesciences	Page 6 of 13
	Title	Statistical Analysis Plan for PASCAL Registry				

under commercial usage and will serve as a mechanism to collect clinical data to further characterize the safety, performance and effectiveness of the PASCAL Transcatheter Valve Repair System.

A description of each study visit and required study procedures is included in the clinical protocol Section 4: Procedures and Methods.

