3.3 Secondary Measures

1. Adverse event assessment (all follow up visits)
2. EQ-5D-5L or KCCQ at baseline, 30 days and 12 months, if available
3. 6MWT at baseline, 30 days, and 12 months, if available
4. NYHA assessment at baseline, 30 days and 12 months, if available

 Edwards	Revision Date: August 22, 2019		Rev	1.0	For Use Only by Affiliates of Edwards Lifesciences	Page 7 of 13
	Title	Statistical Analysis Plan for PASCAL Registry				

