6.2 Handling of Missing Data

All statistical analysis on the endpoints will be performed using only those patients with available data required for endpoint analysis.

Partial onset event dates are imputed for safety data using the result in the earliest event date possible. This imputation will only be performed as needed such as date variable is used in the variable derivation. However, no imputed dates will be presented in the listings.

 Edwards	Revision Date: August 22, 2019		Rev	1.0	For Use Only by Affiliates of Edwards Lifesciences	Page 10 of 13
	Title	Statistical Analysis Plan for PASCAL Registry				

- If the adverse event year is unknown, then the date will be imputed using the procedure date
- If the adverse event month is unknown, then:
 - If the adverse event year matches the year of the procedure date, then impute the month and day using the procedure date
 - Otherwise, assign 'January'
- If the adverse event day is unknown, then:
 - If the adverse event month and year match the month and year of the procedure date, then impute the day using the procedure date
 - Otherwise, assign '01'

For missing data due to patient withdrawal or lost to follow-up in the analyses of time-dependent endpoints, including the primary safety measures, primary performance measure, and secondary measures, the censoring mechanism will automatically account for censored data in the Kaplan-Meier analysis.

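### As worded, SAP 8.3 excludes incomplete patients from the whole quality-of-life analysis, not only from the paired changes, so observed scores drop out of the visit summaries

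*SAP*

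**What the plan says.** SAP 8.3, under functional and quality-of-life measures, first names what is reported: "EQ-5D and KCCQ overall summary scores, and their changes from baseline to 30 days and 12 months will be summarized". The next sentence sets the exclusion: "Patients that are missing a baseline or follow up values will be excluded from the analysis". It names no visit, no instrument and no type of analysis.

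For NYHA class and for 6MWT, the same section uses a narrower rule: "Patients that are missing baseline or follow-up values will be excluded from the paired analysis".

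The general missing-data rule in SAP 6.2 reads: "All statistical analysis on the endpoints will be performed using only those patients with available data required for endpoint analysis". The measure itself is defined in SAP 3.3 as "EQ-5D-5L or KCCQ at baseline, 30 days and 12 months, if available". On patients who leave early, Protocol 3.7 says: "All data collected up until the time of withdrawal will be analyzed". SAP section 10 reports no changes from the protocol's analyses, and Protocol section 8 contains no quality-of-life exclusion.

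**The concern.** Two kinds of result are planned: scores at each visit and changes from baseline. A change needs two values, so leaving out incomplete pairs there is unavoidable. A visit summary needs one. By excluding incomplete patients from the analysis as a whole, the sentence takes valid scores out of summaries that do not need the missing value.

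The loss need not be neutral. A patient with a baseline score and no follow-up score may have died, withdrawn, or been too ill to attend. If such patients started with lower scores, removing them raises the baseline mean, and the table then describes survivors and attenders rather than the treated patients.

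There is also a reproducibility problem. Two programmers could follow this sentence in good faith and report different denominators and means, including at baseline. SAP section 1 makes these analyses the basis of the study report, and no quality-of-life sensitivity analysis is planned that would expose the difference.

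**Working it through.** **Step 1: what the sentence can mean.** The wording allows three readings.

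1. Visit-by-visit pairing for the changes only. All observed scores stay in the visit summaries.
2. Visit-by-visit pairing that also restricts the score summaries to patients with both values.
3. All three visits required before a patient enters any quality-of-life result.

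Reading 1 needs the word *paired*, which the NYHA and 6MWT sentences have and this one lacks. Reading 2 is the literal sense of the sentence. Reading 3 is possible because no visit is named, but nothing states it.

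**Step 2: inputs.** The only document figure is the planned size: "A minimum of 200 patients will be enrolled in the registry at over 10 sites in the Europe". The documents give no quality-of-life completion rate, SD or dropout rate, so there is no plan figure to reproduce. Everything below is assumed: baseline score in 80–90% of patients; 30-day score in 70–90%, independent of having a baseline score; 12-month score in 50–80% of those with the first two; SD 20 points.

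**Step 3: loss under reading 2 (rule keyed to the 30-day visit).** Baseline scores observed = 200 × P(baseline). Kept = 200 × P(baseline) × P(30-day).

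| Baseline / 30-day rate | Observed | Kept | Dropped |
|---|---|---|---|
| 90% / 90% | 180 | 162 | 18 |
| 90% / 80% | 180 | 144 | 36 |
| 80% / 70% | 160 | 112 | 48 |

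Fewer would be dropped if any one follow-up score were enough.

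**Step 4: tilt under reading 2.** With a normal latent propensity to have a follow-up score, the shift in the baseline mean is ρ × φ(c)/r × SD. Here r is the share with a follow-up score, c = z(1 − r), and ρ is the correlation between baseline score and that propensity.

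- φ(c)/r: r = 0.9 gives 0.1755/0.9 = 0.195; r = 0.8 gives 0.2800/0.8 = 0.350; r = 0.7 gives 0.3477/0.7 = 0.497.
- ρ = 0: no shift.
- ρ = 0.1: 0.1 × 20 × (0.195, 0.350, 0.497) = 0.4, 0.7, 1.0 points.
- ρ = 0.3: 0.3 × 20 × (0.195, 0.350, 0.497) = 1.2, 2.1, 3.0 points.

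The direction follows only if lower scorers are the ones without follow-up. A follow-up score discarded for want of a baseline costs precision but has no obvious direction.

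**Step 5: reading 3, for scale only.** 30-day pairs are multiplied by the share who also have a 12-month score. The standard error of the mean grows by √(1/r), where r is now that share.

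| Baseline / 30-day / 12-month rate | 30-day pairs | With 12-month score | SE ratio |
|---|---|---|---|
| 90 / 90 / 80% | 162 | 130 | 1.12 |
| 90 / 80 / 70% | 144 | 101 | 1.20 |
| 80 / 70 / 60% | 112 | 67 | 1.29 |
| 80 / 70 / 50% | 112 | 56 | 1.41 |

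The Step 4 formula, with ρ now linking the 30-day change to having a 12-month score, gives no shift at ρ = 0. At ρ = 0.3 and SD 20 it gives 2.1 points (80% retained) to 4.8 points (50% retained). Under readings 1 and 2 this shift in the 30-day change is zero.

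**The case against.** The best defence is that the sentence is loose drafting and visit-by-visit pairing was meant. SAP 6.2 admits patients who have the data an endpoint requires, and a 30-day change requires only baseline and 30-day values. The exclusion directly follows a sentence naming two separate changes. A fully literal rule would even drop patients who completed one instrument and not the other, although the measure is defined as either one; that can hardly be intended.

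A reader might infer that the 30-day result depends on still having a 12-month score. The documents do not support that as the rule. No sentence says it, and the contrast with NYHA and 6MWT does not show it: those sentences name no visit either. The word *paired* decides whether score summaries are restricted, not whether a later visit is needed at an earlier one.

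A reader might also see a flat contradiction of Protocol 3.7. That passage concerns data collected before withdrawal, not a missed questionnaire, and does not require every value to enter every table. The tension exists only under readings 2 and 3, and only for patients who withdrew.

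Nor can the tilt be sized from the 26.2% annual mortality in Protocol 1.2, which comes from conservatively treated patients with mostly severe functional regurgitation. The documents give no 12-month mortality for this device.

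Finally, restricting all summaries to the same patients has some merit, because baseline and follow-up means then compare like with like. The paired change already serves that purpose. SAP 6.1 also lists sample size in continuous summaries, so a fall in n would be visible, though not its cause.

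These points dispose of the stronger readings. They do not supply the missing limit on the exclusion: SAP 6.2 does not say which data a quality-of-life score summary requires, and the only specific rule is the sentence at issue.

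**Conclusion.** The point holds as a defect of scope. As worded, the quality-of-life rule removes observed scores from the visit summaries, unlike the NYHA and 6MWT rules beside it, and can tilt those summaries towards patients who survived and attended. A restriction of the 30-day change to 12-month completers is a possible but unlikely reading.

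The 18 to 48 dropped baseline scores, and the shift of 0 to 3 points, rest wholly on assumed completion rates, SD and correlation. If missing follow-up is unrelated to the score, there is lost precision and no tilt.

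The consequence is modest. The measure is secondary and collected only where available, and the Protocol synopsis states: "No predefined statistical hypothesis testing will be performed". No decision rule depends on it. The sentence should still be corrected, because it affects what is reported and costs almost nothing to change.

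**What to change.** Replace the quality-of-life exclusion sentence in SAP 8.3 with: *For each instrument and each follow-up visit, patients with a baseline value and a value at that visit on the same instrument enter the paired change at that visit; all available scores enter the visit summaries.* Report n for each instrument, visit and type of summary.

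This brings quality of life into line with NYHA and 6MWT, settles the one-instrument-or-both question, and removes any tension with Protocol 3.7. It needs no new data.

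The cost is that the 30-day and 12-month changes will describe slightly different patients, which n per visit makes visible. It does not cure ordinary available-case selection: a 12-month summary still describes only those alive and assessed. Tabulating reasons for missing scores, including death, and showing baseline and 30-day scores by 12-month availability would let readers judge that.

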1.2 Anatomy and Pathophysiology of Mitral Regurgitation

The mitral valve is an atrioventricular valve, separating the left atrium from the left ventricle (Figure 1). In the normal mitral valve, mitral leaflets coapt during systole to prevent backflow of blood into the left atrium. The mitral apparatus consists of the mitral annulus, mitral leaflets, chordae tendinae, and papillary muscles. The valve itself is saddle-shaped and is a dynamic anatomical structure during the cardiac cycle, playing a crucial role in proper mitral valve coaptation.

[figure not shown]

Figure 1. The Anatomy and Structure of the Mitral Valve and Mitral Apparatus^{5,6}

Initially in MR, patients experience a prolonged asymptomatic period, and if left untreated, may progress to moderate and then severe MR with symptoms such as decreased exercise tolerance and exertional dyspnea.² Eventually, chronic MR imposes volume overload on the left ventricle, which results in cyclical worsening of progressive left ventricular (LV) dilatation, LV remodeling, and cardiomyopathy. This may lead to worsening LV failure, pulmonary hypertension, atrial fibrillation and increased mortality.¹ Although MR may be tolerated for a long time in some patients, in others, the progression of heart failure with LV dysfunction may be more rapid.⁷ The natural course of severe MR depends on many factors including, but is not limited to, the type of MR, the presence of symptoms, LV function and the presence of atrial fibrillation or pulmonary hypertension.⁸ A study of 953 patients with mostly severe FMR (who were considered too high risk for surgery) and were treated with conservative therapy found an annual mortality rate of 26.2%.⁹ Similarly, in high surgical risk patients with severe DMR and NYHA Class III/IV symptoms, annual mortality has been reported to be as high as 34%.¹⁰ The risk of death in subjects aged ≥ 70 years old with moderate or severe MR has been shown to be more than four-fold higher than that of age- and sex-matched subjects with absent or mild MR.¹¹

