1.7 Prior Clinical Experience With the PASCAL System

1.7.1 *Compassionate Use Experience of the PASCAL System in Treating Mitral Regurgitation*

Praz et al. (2017) published the 30-day results of the PASCAL System in an early feasibility, first-in-man, compassionate use experience of 23 patients with severe MR with either FMR (52%) or DMR (26%) or mixed etiologies (22%). Despite the anatomical complexity of this compassionate use population, technical success was 96% while device success was in 76% of the cohort. The 6-month results with 29 patients (28% DMR) were presented by Webb (2017)⁷⁸ and demonstrated high rates of MR $\leq 2+$ (95%) and NYHA I/II functional status (100%) and a low rate of second device requirement (25%). Major adverse events were low in this high risk/inoperable population; mortality was 0% and 10% during the procedure and at 30 days, respectively.⁷⁸ These early results demonstrate the safety and feasibility of TMVr with the PASCAL System in patients with complex anatomies and suggests that the device addresses an unmet clinical need in both DMR and FMR patients.⁷⁶

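### The NYHA class summary and shift table have no place for patients who died, so both describe only survivors with an NYHA value; deaths should be shown in the same table.

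*SAP*

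**What the plan says.** NYHA class at baseline, 30 days and 12 months is a secondary measure, collected where available (Protocol 3.2.3, SAP 3.3). SAP 8.3 plans two displays:

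- An unpaired summary: "Count and percentage of patients in each NYHA Class will be summarized".
- A paired one: "Change from baseline will be presented as a shift from baseline to 30-day and 12-month follow-up". Its exclusion rule follows: "Patients that are missing baseline or follow-up values will be excluded from the paired analysis".

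The exclusion sentence names only the paired analysis. For the unpaired summary the rule comes from SAP 6.2: "All statistical analysis on the endpoints will be performed using only those patients with available data required for endpoint analysis".

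Protocol 3.7 introduces its exit list with "Patients may exit the registry for any of the following reasons", and death is on that list. No part of SAP 8.3, SAP 6.2 or Protocol 8 gives NYHA a death category, a worst class for the dead, or a denominator that keeps them.

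Deaths are reported in two other places. SAP 8.1 gives each component of the 30-day major adverse event composite, including all-cause death, with a 95% confidence interval. SAP 9.1 tabulates primary cause of death at 30 days and 1 year.

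**The concern.** A patient who has died has no NYHA class at the visit, so under these rules the death is handled like any other missing value. It is mixed with withdrawals, losses to follow-up and assessments that were simply not done.

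This is a single-arm registry without hypothesis tests, so the descriptive tables are the result and no control arm shares the attrition. The change in NYHA class by 12 months is likely to be read as the functional benefit of treatment. A reader of the planned tables cannot see from which baseline class patients died, or what share of those treated were alive and in a good class at 12 months.

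SAP 8.3 already deals with a similar problem for another functional measure: a patient medically unable to do the six-minute walk is scored 0 m. NYHA has no counterpart. Because NYHA is ordinal and shown as a table, death can be displayed as its own category without assigning it a number.

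**Working it through.** The documents give no NYHA target, effect size or precision, and the minimum of 200 patients has no calculation behind it. There is no stated figure to reproduce.

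**Step 1: does another rule catch the deaths?** SAP 6.2 says that for withdrawal and loss to follow-up "the censoring mechanism will automatically account for censored data in the Kaplan-Meier analysis". That sentence does not name death, and censoring cannot operate in a class count or a shift table. The death tables in SAP 8.1 and 9.1 are not broken down by baseline NYHA class. Nothing else applies.

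**Step 2: what deaths do to each display.** Invented example: 200 patients at baseline, 140 in class III and 60 in class IV. By 12 months 40 have died, and no survivor changes class.

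| Display | Baseline | 12 months, all 40 deaths in class IV | 12 months, deaths in proportion (28 in III, 12 in IV) |
|---|---|---|---|
| Unpaired, class IV | 60/200 = 30% | 20/160 = 12.5% | 48/160 = 30% |
| Unpaired, class III | 140/200 = 70% | 140/160 = 87.5% | 112/160 = 70% |
| Paired shift, unchanged | not applicable | 160/160 | 160/160 |

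The unpaired percentages can move through deaths alone, but only if deaths concentrate in the high classes. The paired table shows no false improvement in either case. What it omits is that, in the first scenario, 40 of the 60 patients in the class IV row died: the planned row shows 20/20 unchanged.

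**Step 3: how far apart the two summaries can be.** Let p be the share of survivors in class I/II and m the mortality by 12 months. The share alive and in class I/II is p × (1 − m), and the gap from p is p × m. Inputs: N = 200 (the planned minimum); p = 0.80, m = 0.10 and m = 0.20 (all assumed); every survivor has an NYHA value (assumed). Exact binomial 95% intervals are in brackets.

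- m = 0.10: 20 deaths, 180 survivors, 0.80 × 180 = 144. Among survivors 144/180 = 80.0% (73.4 to 85.6); among all 144/200 = 72.0% (65.2 to 78.1). Gap 8 points.
- m = 0.20: 40 deaths, 160 survivors, 0.80 × 160 = 128. Among survivors 128/160 = 80.0% (73.0 to 85.9); among all 128/200 = 64.0% (56.9 to 70.6). Gap 16 points.

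With p from 0.70 to 0.90 the gap is 7 to 9 points at 10% mortality and 14 to 18 points at 20%.

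**Step 4: the same pattern in the protocol's background.** Protocol 1.7.1 reports 100% in NYHA I/II at 6 months in a 29-patient compassionate-use series, and in the same account "mortality was 0% and 10% during the procedure and at 30 days, respectively". If that 10% means 3 of the 29 (an assumption; 3/29 = 10.3%), at most 26/29 = 89.7% could have been alive and in class I/II.

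**The case against.** The strongest counter-argument is that nothing is hidden. The paired exclusion is stated openly, NYHA is reported as counts as well as percentages, and deaths are tabulated for the same periods. A reader can see how many died. What is missing is a joint display, on one of several secondary measures with no threshold or decision attached. This stands as a limit on importance. It does not remove the gap, because the separate tables cannot be linked to baseline class.

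A reader might also infer more than the documents support:

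- *That the shift table shows improvement produced by deaths.* It does not. Each survivor is compared with his or her own baseline. Only the unpaired percentages can behave this way, and the documents give no evidence that deaths will concentrate in the highest baseline classes.
- *That the NYHA result is overstated by a known number of points.* The survivor percentage and the percentage alive and in class I/II answer different questions, and the gap between them is p × m by construction. The SAP defines no NYHA responder, failure or percentage worsened, so no planned figure is wrong.
- *That the protocol's mortality figures predict this registry.* Protocol 1.2 describes patients who were "treated with conservative therapy found an annual mortality rate of 26.2" per cent, and they did not receive this device. The 10% in Protocol 1.7.1 is a 30-day figure from a small high-risk or inoperable group. This registry enrols elective commercial patients. Where data are retrospective, Protocol 4.3 requires consent before any are collected, so those patients must have survived to consent, which would lower recorded mortality.
- *That everyone without a value is either dead or known to be alive.* Under Protocol 3.7 no further data are collected after withdrawal, and a search of death registries is optional. Some patients will have unknown vital status.

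**Conclusion.** The point holds as an inexpensive improvement to the display. Both planned NYHA summaries describe survivors with an NYHA value, and patients who died appear in no cell. The unpaired percentages may look better through loss of patients in high classes. The paired shift stays valid for those it includes but leaves out the worst outcomes.

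The size cannot be fixed from the documents, because 12-month mortality in this registry is not given. The 72% and 64% shown above rest on an assumed 80% of survivors in class I/II, assumed mortality of 10% and 20%, and complete NYHA data in survivors. They show how far two legitimate summaries can differ. They are not an estimate of bias. No hypothesis test, power or error rate is involved.

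**What to change.** In SAP 8.3, for the 30-day and 12-month NYHA shift tables:

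1. Add three columns: *died before visit*; *known alive, not assessed*; and *withdrawn or lost, vital status unknown*. The third column prevents withdrawn or lost patients from being counted as alive.
2. Use all patients with a baseline NYHA class as the row denominator.
3. Beside the planned paired results, report the percentage known alive and in NYHA I/II.
4. Keep the planned paired analysis and the unpaired class percentages, and label both as survivors with data.

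Because patients of unknown vital status stay in the denominator, the percentage in item 3 is a lower figure. The separate columns let the reader see how much of the shortfall is death and how much is missing information.

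The cost is a few table columns and a short addition to the SAP. Exit reasons are already documented under Protocol 3.7, and SAP 9.1 already requires deaths to be placed at 30 days and 1 year, so no new data collection should be needed. The downside for the sponsor is that a less favourable NYHA figure will stand beside the planned one.
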